Analgesic and Antioxidant Effects of Melatonin in Pediatric Surgery

Protocol Version

v. 1.0

Date:

September 15th 2020

1. Introduction

Pediatric patients undergoing surgery are at significant risk for experiencing postoperative pain. Studies have shown a high prevalence of pain and behavioral problems that can persist for several weeks after surgery. The memory of perioperative pain in children can be distressing and have lasting consequences. Children who develop negatively biased pain memories are more likely to experience poorer pain outcomes in the future. Research has shown that children with such memories experience increased postoperative pain several days after surgery. In addition, inadequate management of acute postoperative pain may contribute to problems such as postoperative bleeding and impaired recovery. These findings underscore the importance of effectively managing postoperative pain to potentially prevent the formation of negatively biased pain memories in young children. In addition, acute pain activates the nociceptive system and triggers a stress response involving the sympathetic nervous system and the hypothalamic-pituitary-adrenal axis. This cascade leads to cerebral, autonomic, and hormonal responses and induces changes in several biochemical processes. Pain has been shown to be associated with oxidative stress (OS) in response to tissue injury, inflammation, and cytokine production.

Melatonin, a neurohormone produced by the pineal gland, plays a role in the nociceptive modulation of various types of pain. Melatonin has anti-inflammatory and antioxidant properties. Early oral

administration of melatonin in infancy has been shown to significantly reduce plasma levels of OS biomarkers such as total hydroperoxides and advanced oxidation protein products.

High levels of these OS biomarkers have been observed in neonates with high pain scores, demonstrating a strong relationship between pain and OS. Melatonin shows a potential role in protecting neonates undergoing surgery from the deleterious effects of OS. After administration of exogenous melatonin, a significant reduction in lipid and protein peroxidation in the postoperative period has been reported in neonates. Recently, Song et al. reported that sirtuin 1 (SIRT1) also plays a critical role in the pathogenesis of pain, showing analgesic effects in chronic pain conditions such as neuropathic and inflammatory pain.

Several studies have shown that lipid peroxidation is involved in different types of pain, such as cancer pain, fibromyalgia, and neuropathic pain. 4-HNE plasma levels are good indices of free radical damage on lipids. Lipid damage from free radical exposure leads to lipid hydroperoxide generation from lipids and to carbonyl formation and protein hydroperoxide generation from proteins. Lipid peroxidation reaction leads to increased endogenous production of reactive aldehydes and their derivatives, such as malondialdehyde and 4-HNE²⁰. Malondialdehyde is the most mutagenic by-product of lipid peroxidation, while 4-HNE is the most toxic. 4-HNE is often used as a marker of OS and has been implicated in the pathogenesis of cancer, neurodegenerative diseases, diabetes, and other diseases. 4-HNE is involved in many pathophysiological signaling pathways SIRT1, acting as a NAD⁺-dependent deacetylase, plays a crucial role in critical cellular functions such as energy metabolism, genomic stability, inflammation, and immune response. Due to its multifunctional role, SIRT1 has been considered a promising target for therapies aimed at treating various conditions, including metabolic disorders and age-related diseases. Decreased SIRT1 levels have been observed in the spinal cord of various pathological pain models, in which SIRT1 activation helped alleviate chronic pain by regulating inflammation, oxidative stress, and mitochondrial dysfunction.

Recent animal studies have demonstrated that miRNAs are involved in pain processing pathways. Ikuma et al. found the increased extracellular release of microRNAs from dorsal root ganglion cells in a rat model of neuropathic pain.

In this prospective, randomized, double-blind pilot study, we test the hypothesis that melatonin, administered as premedication before induction of anesthesia, reduces OS and postoperative pain involving the sirtuin pathway in children undergoing minor abdominal surgery.

The relationship between pain and 4-HNE, between 4-HNE and melatonin levels, and between microRNAs and SIRT1 levels will be investigated.

2. Methods

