2.1 Recruitment and Randomization

The trial is approved by the local Ethics Committee (LocalNo.125222022) according to the Helsinki Declaration of 1964. Patients' legal guardians will provide written informed consent.

Fifteen Children between 3 and 5 years of age scheduled for elective surgery will be prospectively enrolled at the Department of Pediatric Surgery, University Hospital of Messina, Italy. Inclusion criteria are the need for elective surgery, in the morning time. Exclusion criteria are children with cerebral malformations and/or injuries, or surgery in the afternoon or at night to eliminate conditions that could affect melatonin production. Children will be also excluded in cases of withdrawal of informed consent, insufficient blood samples, and hemolysis of the blood sample, as hemolysis interferes with the biochemical determination of the OS biomarkers.

Infants matching the clinical criteria for inclusion in the study will then be randomized to be premedicated with oral melatonin (Mel group) or 5% dextrose (Control group)

Permuted, block randomization will be performed by a biostatistics using computerized sequences, and group assignments will be provided in concealed opaque envelopes. Parents of participants will be informed of their infant's group allocation at discharge.

Interventions

- *Mel group:* Melatonin (Dicoson, Dicofarm, Italy, 5 drops = 1 mg) will be administered orally.

The product is listed in the Register of Dietary Supplements on the website of the Ministry of Health (<http://www.ministerosalute.it/alimenti/dietetica>) and is classified with the following code: 943314283. This product is subject to the European Directive on Foodstuffs according to DL n. 169 of May 21, 2004, and not to the European Directive on Medicines 2001/20/EC transposed at the Italian level with D.L. n. 211 of June 24, 2003. Melatonin administration has a good safety profile, with no known adverse effects. Approximately 1 hour before induction of anesthesia, patients will receive oral melatonin or placebo. Mel treated children received a single dose of oral melatonin 0.5 mg/kg (for a max 10 mg). Melatonin (Dicoson, Dicofarm, Italy) will be prepared by a dedicated resident in a fixed volume of 5 mL by adding water to a syringe without a needle.

- *Control group:* Approximately 1 hour before induction of anesthesia, patients will receive 5 mL of 5% dextrose (placebo), used to simulate the sweet taste of the melatonin formulation.

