2.4 Melatonin, 4-Hydroxynonenal, and SIRT1 Measurements

Samples of 0.2 mL of plasma will be collected at T0 (pre-hospitalization, 1 day before surgery), T1 (after anesthesia, immediately before surgery) and T2 (at 1 h after the end of the surgery and awakening after anesthesia), and biochemical analyses will be performed.

Melatonin plasma levels will be assessed at each experimental time point (T0, T1, T2) using a competitive enzyme-linked immunosorbent assay (cELISA) kit from Antibodies.com (A87093) according to the manufacturer's instructions. T1 and T2 plasma samples from Mel treated children suspected of containing concentrations higher than the highest standard (500 pg/mL) will be diluted 1:100 (v/v) with sample diluent prior to analysis. Color development will be monitored at 450 nm in a Thermo Scientific (MultiSkan FC) microplate reader, and a standard curve (range 7.813-500 pg/mL) will be generated using a four-parameter logistic (4-PL) curve fit.

4-Hydroxynonenal (4-HNE) as a marker of lipid peroxidation will be measured to evaluate OS by using a cELISA kit from Antibodies.com (A86962). Plasma concentrations will be calculated by reading the absorbance at 450 nm and referring to the standard curve (range 31.25-2000 pg/mL). SIRT1 will be quantified using an ELISA kit from Invitrogen (EH427RB). Plasma samples will be diluted 1:2 as indicated by the Manufacturer before analysis. SIRT1 concentrations will be calculated by absorbance reading at 450 nm and referring to the standard curve (range 1.23-300 ng/mL).

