2.6 Data analysis

Data will be expressed as mean (standard error, SE) or median (interquartile range, Q1-Q3) as appropriate. Differences between T0, T1, and T2 will be analyzed by repeated measures ANOVA followed by Tukey's multiple comparison test for melatonin, 4-HNE, miR34 and miR124a plasma levels, while by Friedman test followed by Dunn's test in the case of SIRT1 levels. At each experimental time point, comparisons between the Control and Mel treated children will be performed using Student's t-test for unpaired data or Mann-Whitney U test as appropriate. Linear regression analyses will also be performed to examine correlations between variables (Pearson correlation). All data with P < 0.05 will be considered statistically significant. GraphPad Prism 6.0 (GraphPad Software, Inc., San Diego, CA, USA) will be used for statistical analysis.

References

Fischer S, *et al.* Role of anxiety in young children's pain memory development after surgery. *Pain* 160, 965-972 (2019).

Perrone S, *et al.* Oxidative Stress as a Physiological Pain Response in Full-Term Newborns. *Oxid Med Cell Longev* 2017, 3759287 (2017).

Marseglia L, *et al.* Antioxidant Effect of Melatonin in Preterm Newborns. *Oxid Med Cell Longev* 2021, 6308255 (2021).

Perrone S, *et al.* Melatonin in Newborn Infants Undergoing Surgery: A Pilot Study on Its Effects on Postoperative Oxidative Stress. *Antioxidants (Basel)* 12, (2023).

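### The hypothesis invokes the sirtuin pathway, but the plan specifies no arm-adjusted link between SIRT1 and 4-HNE or pain, so pathway involvement cannot be told from parallel change

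*Combined protocol and SAP*

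**What the plan says.** The Introduction states the hypothesis that premedication with melatonin "reduces OS and postoperative pain involving the sirtuin pathway in children undergoing minor abdominal surgery". The sentence that follows lists the relationships of interest: "The relationship between pain and 4-HNE, between 4-HNE and melatonin levels, and between microRNAs and SIRT1 levels will be investigated".

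Section 2.4 sets the sampling: "Samples of 0.2 mL of plasma will be collected at T0 (pre-hospitalization, 1 day before surgery), T1 (after anesthesia, immediately before surgery". A third sample, T2, follows one hour after surgery and awakening. Melatonin, 4-HNE and SIRT1 are all assayed under this scheme. Section 2.5 limits the microRNA analyses to N=3 at each time point.

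Three parts of Section 2.6 bear on SIRT1:
- Change over time is tested "while by Friedman test followed by Dunn's test in the case of SIRT1 levels".
- Arms are compared without naming the variables: "At each experimental time point, comparisons between the Control and Mel treated children will be performed using Student's t-test for unpaired data or Mann-Whitney U".
- Associations are covered by one general sentence: "Linear regression analyses will also be performed to examine correlations between variables (Pearson correlation"). It gives no pairs, no time points and no adjustment for arm.

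The significance rule is "All data with P < 0.05 will be considered statistically significant". Section 2.1 sets the size: "Fifteen Children between 3 and 5 years of age scheduled for elective surgery will be prospectively enrolled". The allocation ratio is not given.

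**The concern.** The hypothesis says more than that melatonin changes several markers. It says that the fall in oxidative stress and pain involves SIRT1. Supporting that needs some analysis in which SIRT1 is related to 4-HNE or to pain.

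The three named relationships fall into two groups, pain with 4-HNE with melatonin level, and microRNAs with SIRT1. No named pair joins the groups, and the one partner given to SIRT1 is the variable with the fewest samples.

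Two routes to a pathway statement remain open. One is to observe that SIRT1 and 4-HNE each differ between arms. The other is to use the general correlation sentence for an unadjusted Pearson test of SIRT1 against 4-HNE over all children. Both can give a positive result when melatonin moves the two markers by separate routes. The trial could then attribute an effect to the sirtuin pathway on evidence that does not bear on it.

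**Working it through.** The plan gives no power calculation or effect size, so there is no figure of its own to reproduce.

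**Inputs.** From the documents: 15 children (Section 2.1) and P < 0.05 (Section 2.6). Assumed: two-sided tests, a 7 v 8 split, normal data, one T2 value per child, and melatonin shifting SIRT1 up and 4-HNE down by d within-arm SD. Simulations used 20,000 trials per scenario.

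**1. Correlation created by the arm effect alone.** Suppose SIRT1 and 4-HNE are unrelated within arms. With p = 7 × 8 / 15² = 0.249, the pooled correlation has size p·d² / (1 + p·d²).
- d = 1: 0.249 / 1.249 = 0.20
- d = 1.5: 0.560 / 1.560 = 0.36
- d = 2: 0.996 / 1.996 = 0.50

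**2. Critical values.** r = t / √(df + t²). The pooled Pearson test has 13 df and t = 2.160, so r = 2.160 / √(13 + 4.67) = 0.514. The arm-adjusted partial correlation has 12 df and t = 2.179, so r = 2.179 / √(12 + 4.75) = 0.532.

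**3. Rejection rates with no within-arm link.**

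| Shift d (SD) | Both arm t-tests P < 0.05 | Pooled Pearson P < 0.05 | Arm-adjusted P < 0.05 |
|---|---|---|---|
| 1 | 19% | 11% | 5% |
| 1.5 | 58% | 28% | 5% |
| 2 | 89% | 56% | 5% |

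The pooled test reacts to the shared arm effect. The adjusted test does not.

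**4. How far two arm differences discriminate.** This depends on how the effect on 4-HNE arises. Rates are for both t-tests significant, at shifts of 1, 1.5 and 2 SD.
- Same direct effect on 4-HNE whether or not a link exists: 19%, 58%, 89% with no link, against 30%, 66%, 92% with within-arm r = −0.7.
- Effect on 4-HNE passing only through SIRT1: 2%, 4%, 5% at r = 0, against 19%, 44%, 70% at r = 0.7 in size.

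Two arm differences are therefore weak evidence where melatonin may also act on 4-HNE directly. They are informative only if that direct route is ruled out beforehand, and the plan does not rule it out.

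**5. Whether the arm-adjusted correlation is enough alone.** It is not. If melatonin leaves SIRT1 unchanged but the markers covary between children at r = −0.7, it is significant in about 85% of trials. An arm effect on SIRT1 must be required as well.

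**6. Precision.** On normal data the adjusted test has about 85% power at within-arm |r| = 0.7 and 47% at 0.5. With SIRT1 ranked, in line with its non-parametric treatment in Section 2.6, these become about 80% and 42%. For an observed partial r of 0.5, Fisher's z is 0.549 ± 1.96 / √11, giving a 95% CI of about −0.04 to 0.81.

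**The case against.** A reader might infer that no planned test connects SIRT1 with melatonin at all. The documents do not support that. The arm comparisons in Section 2.6 are not restricted to particular variables, so on a plain reading they include a randomised test of melatonin's effect on SIRT1.

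A reader might also infer that a SIRT1 v 4-HNE or SIRT1 v pain analysis is excluded. It is not. The general correlation sentence could admit either, so the link is unspecified rather than ruled out. That does not rescue the plan. The Introduction does name pairs and leaves these out, and the analysis most readily read from Section 2.6 is the unadjusted one with the error rates shown above.

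It is tempting to say that significant arm differences hardly distinguish a pathway from its absence. That holds only where melatonin has the same direct effect on 4-HNE in both cases. Where the whole effect passes through SIRT1, they discriminate well.

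Finally, this is described as a pilot study, and no passage states that pathway involvement will be concluded from two arm differences. That is fair: the risk lies in what the plan permits. The pilot label supports calling the analysis exploratory, but does not remove the mismatch between the hypothesis and the tests.

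**Conclusion.** The point holds in this form: the sirtuin part of the hypothesis has no pre-specified analysis relating SIRT1 to 4-HNE or to pain, and no planned correlation is adjusted for arm. The planned tests therefore cannot separate pathway involvement from parallel change. If melatonin shifts both markers independently by 1, 1.5 or 2 SD, an unadjusted pooled Pearson test is significant in about 11%, 28% or 56% of trials, against about 5% after adjustment. These figures rest on the assumed 7 v 8 split, normal data, two-sided tests and shift sizes; the documents give none of these. Neither the arm comparisons nor the adjusted correlation is sufficient alone. Even together they would show consistency with a pathway, not mediation.

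**What to change.** In the Introduction and Section 2.6, name SIRT1 v 4-HNE at T2, one value per child, as an exploratory association adjusted for arm (a partial correlation, or a regression of 4-HNE on SIRT1 and arm). Rank SIRT1 and report the estimate with its 95% CI.

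Add a rule for interpretation. Results are described as consistent with sirtuin involvement only if SIRT1 and 4-HNE both differ between arms and the arm-adjusted association supports it, and never as proof of mediation. Otherwise they are reported as concurrent changes. The alternative is to limit the hypothesis to an effect of melatonin on SIRT1 levels.

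A matching SIRT1 v FLACC analysis can be added only after one FLACC value per child has been defined, because Section 2.3 fixes neither a scoring time nor a summary score.

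The cost is some wording and one extra analysis on data already to be collected, and a more cautious conclusion. With 15 children the partial r must exceed about 0.53 to reach significance. Power of the ranked test is about 80% at within-arm |r| = 0.7 and 42% at 0.5, and lower still once the arm differences are also required.

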2.1 Recruitment and Randomization

The trial is approved by the local Ethics Committee (LocalNo.125222022) according to the Helsinki Declaration of 1964. Patients' legal guardians will provide written informed consent.

Fifteen Children between 3 and 5 years of age scheduled for elective surgery will be prospectively enrolled at the Department of Pediatric Surgery, University Hospital of Messina, Italy. Inclusion criteria are the need for elective surgery, in the morning time. Exclusion criteria are children with cerebral malformations and/or injuries, or surgery in the afternoon or at night to eliminate conditions that could affect melatonin production. Children will be also excluded in cases of withdrawal of informed consent, insufficient blood samples, and hemolysis of the blood sample, as hemolysis interferes with the biochemical determination of the OS biomarkers.

Infants matching the clinical criteria for inclusion in the study will then be randomized to be premedicated with oral melatonin (Mel group) or 5% dextrose (Control group)

Permuted, block randomization will be performed by a biostatistics using computerized sequences, and group assignments will be provided in concealed opaque envelopes. Parents of participants will be informed of their infant's group allocation at discharge.

Interventions

- *Mel group:* Melatonin (Dicoson, Dicofarm, Italy, 5 drops = 1 mg) will be administered orally.

The product is listed in the Register of Dietary Supplements on the website of the Ministry of Health (<http://www.ministerosalute.it/alimenti/dietetica>) and is classified with the following code: 943314283. This product is subject to the European Directive on Foodstuffs according to DL n. 169 of May 21, 2004, and not to the European Directive on Medicines 2001/20/EC transposed at the Italian level with D.L. n. 211 of June 24, 2003. Melatonin administration has a good safety profile, with no known adverse effects. Approximately 1 hour before induction of anesthesia, patients will receive oral melatonin or placebo. Mel treated children received a single dose of oral melatonin 0.5 mg/kg (for a max 10 mg). Melatonin (Dicoson, Dicofarm, Italy) will be prepared by a dedicated resident in a fixed volume of 5 mL by adding water to a syringe without a needle.

- *Control group:* Approximately 1 hour before induction of anesthesia, patients will receive 5 mL of 5% dextrose (placebo), used to simulate the sweet taste of the melatonin formulation.

The contents of the syringe will be blindly administered to the patients by the attending nurse, who will not be involved in the study.

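### Section 2.1 excludes conditions that disturb melatonin but none of the diseases the introduction links to 4-HNE, so one such child among 15 could blunt or inflate the 4-HNE comparison

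*Combined protocol and SAP*

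**What the plan says.** Section 2.1 sets the population in a few lines: "Fifteen Children between 3 and 5 years of age scheduled for elective surgery will be prospectively enrolled", and "Inclusion criteria are the need for elective surgery, in the morning time". No health-status requirement is added. The clinical exclusions are: "Exclusion criteria are children with cerebral malformations and/or injuries, or surgery in the afternoon or at night". The reason given is that such circumstances might disturb the child's own melatonin output. Children are also dropped for withdrawn consent, too little blood, or a hemolysed sample, the last because "hemolysis interferes with the biochemical determination of the OS biomarkers".

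The introduction describes the markers more broadly. It says 4-HNE "has been implicated in the pathogenesis of cancer, neurodegenerative diseases, diabetes, and other diseases". On oxidative stress in general: "Pain has been shown to be associated with oxidative stress (OS) in response to tissue injury, inflammation, and cytokine production". SIRT1 "plays a crucial role in critical cellular functions such as energy metabolism, genomic stability, inflammation, and immune response".

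Minor abdominal surgery is named in the hypothesis at the end of the introduction but is not an eligibility criterion. Section 2.4 takes blood at T0 (the day before surgery), T1 and T2. Section 2.6 compares the arms at each time point by t-test or Mann-Whitney. It states no adjustment for T0, no other covariate and no rule for influential values.

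**The concern.** The plan accepts the principle that a condition which distorts a measurement should keep a child out. It applies this to melatonin, and to the marker assay through hemolysis, but not to disease that may move 4-HNE itself, the marker on which the antioxidant hypothesis rests. Limiting enrolment to minor abdominal operations would not close the gap, because that restricts the operation and not the child's underlying disease.

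Randomisation protects against bias on average. With about seven or eight children per arm and no stratification stated, it does not protect a single realised comparison. A child with a disease-driven 4-HNE level shifts that arm's mean and widens the pooled SD. In Mel this can hide a true reduction; in Control it can exaggerate one.

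**Working it through.** The plan gives no power calculation, SD or expected effect for its 15 children, so there is no figure to reproduce. What follows is an illustration.

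**Inputs**
- From section 2.1: 15 children, read as the total.
- From section 2.6: unpaired t-test, 5% level.
- Assumed: arms of 8 (Mel) and 7 (Control), because the ratio is not stated; two-sided test; normal data with SD 1; true melatonin effect a 1.5 SD reduction; one child raised by d = 2 or 3 SD.

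**Shift in the between-arm difference** (d divided by the arm size)
- Child in the arm of 8: 2/8 = 0.25 and 3/8 = 0.375 SD.
- Child in the arm of 7: 2/7 = 0.29 and 3/7 = 0.43 SD.
- Standard error of the difference: √(1/8 + 1/7) = 0.52 SD, so each shift is less than one standard error.

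**Pooled SD** (child in the arm of 7, 13 degrees of freedom)
- Expected pooled variance is 1 + d²(6/7)/13.
- d = 2: 1 + 4 × 0.857/13 = 1.26, SD 1.12 (up 12%).
- d = 3: 1 + 9 × 0.857/13 = 1.59, SD 1.26 (up 26%).

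**Power of the t-test for a 1.5 SD effect** (simulation)

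| Situation | d = 2 | d = 3 |
|---|---|---|
| No such child | 76% | 76% |
| Child in Mel | 51% | 32% |
| Child in Control | 83% | 83% |

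With the child in Control, the expected difference is 1.5 + 0.29 = 1.79 or 1.5 + 0.43 = 1.93 SD, so the extra power comes from an inflated estimate. With the arm sizes reversed, power with the child in Mel is 49% and 29%.

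**False positives.** With no true effect, the t-test rejects in 4% to 5% of runs with such a child present.

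**Chance that such a child enrols**, 1 − (1 − p)^15, for assumed prevalences p:
- 0.1%: 1.5%
- 1%: 14%
- 5%: 54%

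**Power allowing for that chance** (taking one child if any)
- Averaged over allocation: (8/15) × 51 + (7/15) × 83 = 66% for d = 2; (8/15) × 32 + (7/15) × 83 = 56% for d = 3.
- At 1% prevalence: 0.86 × 76 + 0.14 × 66 = 75%, or 0.86 × 76 + 0.14 × 56 = 73%.
- At 5% prevalence: 0.46 × 76 + 0.54 × 66 = 71%, or 0.46 × 76 + 0.54 × 56 = 65%.
- At 0.1% prevalence it stays at about 76%.

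**Use of T0.** If the offset is the same at T0 and afterwards, it cancels in the change from T0. At an assumed correlation of 0.5 between time points, the SD of the change is √(2 × (1 − 0.5)) = 1, so power returns to about 76%.

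**The case against.** Three objections have force.

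First, the size is assumed. The introduction says 4-HNE is implicated in how certain diseases arise. It does not say that affected children have raised plasma 4-HNE, or by how much. Inflammation appears there as a process, not as a diagnosis, so chronic inflammatory disease and acute infection are an extension of the text. This stands: the 2 to 3 SD range is illustrative.

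Second, such children may be rare. Age 3 to 5, elective surgery and the minor abdominal operations named in the hypothesis plausibly point to the lower prevalences, where average power hardly moves. This also stands, although none of these features excludes anyone and the documents give no prevalence.

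Third, the design already limits the harm. Every child has a T0 sample, the within-child analyses across T0, T1 and T2 cancel a stable offset, and the T0 comparison between arms may show an imbalance. This stands in part. The between-arm tests at T1 and T2 make no use of T0. Mann-Whitney caps one child's influence but does not restore power at these offsets: with 7 Mel and 8 Control it falls from 70% to 44% (2 SD) or 31% (3 SD).

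A reader might infer that one such child could dominate the 4-HNE and SIRT1 results, or produce a spurious finding for melatonin. The documents do not support this. In the assumed range the shift is below one standard error and the false-positive rate of the between-arm test is not raised. For SIRT1 the introduction describes cellular functions and spinal-cord levels in pain models; nothing in it ties plasma SIRT1 to any of the diseases it names for 4-HNE.

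**Conclusion.** The gap in the criteria is real and follows from the plan's own text, but the consequence is conditional and minor. It concerns 4-HNE in the T1 and T2 between-arm comparisons. If a child with a relevant disease enrols, the harm is lost power (child in Mel) or an exaggerated difference (child in Control). The figures rest on the assumed 8 v 7 split, a 1.5 SD effect and a 2 to 3 SD offset. How likely the harm is depends on a prevalence that the documents do not give. The change is worth making because it is cheap, not because the trial's conclusions hang on it.

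**What to change.** Add to section 2.1, applied before randomisation: exclusion of known malignancy; diabetes or other metabolic disease; chronic inflammatory or neurodegenerative disease; and acute infection or fever at T0 or on the day of surgery. State that this is determined from the medical history, since the documents describe no pre-operative assessment beyond the T0 blood sample. The cost is a wording change, slightly narrower generalisability and possibly a few ineligible children, which is acceptable in a mechanistic pilot of this size.

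As a complement, amend section 2.6 so that the T1 and T2 between-arm comparisons of 4-HNE are adjusted for the T0 value already collected. This removes much or all of a stable offset, including one from a cause that no exclusion list foresees. It does not remove the effect of an acute illness that begins after T0, which is why the exclusion is still useful. No new sample is needed. If a simple change score is used, its SD exceeds that of the post value when the correlation with T0 is below 0.5, because √(2(1 − ρ)) is then above 1. Covariate adjustment with an estimated slope avoids imposing that penalty.
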